The secondary endpoints of progression of ARF to a different stage as defined by AKIN criteria will be assessed.[3] If a patient is enrolled at stage III ARF, they will be considered to have progressed should they be started on renal replacement therapy (RRT). Other secondary endpoints that will be assessed include change in serum creatinine from baseline to day 14, combined increase of treatment success and “partial response” which we define as serum creatinine level decreased by >50% from baseline but not to baseline without dialysis or HRS recurrence, transplant free survival at day 30 and 180, overall survival at day 30 and 180, composite survival index at day 30 and 180.

**Statistical Methods:** All analyses will be conducted based on the intention to treat population. Results will be expressed as means with standard deviations. Chi-squared and Fisher’s exact test will be used to analyze our categorical endpoints. Student’s t test and Mann-Whitney Rank Sum test will be used for secondary analysis of differences in numerical lab data. Kaplan-Meier curves will be constructed and compared by a log-rank test to assess our secondary endpoints of survival. A p value of <0.05 will be significant. Subgroup analysis will be performed by stratifying on initial AKIN stage.

**Future Study:** If there is a treatment benefit with using PTX for treatment of ARF in patients with cirrhosis, we would apply for an orphan grant from the NIH or foundation awards from the American Association for the Study of Liver Diseases for a multi or single center, randomized, double blinded placebo controlled trial. Ideally we could combine this with translational research to help better determine a mechanism of action.

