## 2. Study Design

[figure not shown]
The proposed study is a blinded prospective, placebo controlled, randomized pilot study. Figure 1 shows the study design schematic. Subjects will be identified during their hospitalization with ARF. Each subject will undergo screening and a pre-dosing history and physical exam, and safety assessment, which will include reviewing basic blood work results and imaging from their hospitalization (CBC, CMP, INR, Blood cultures, UA and urine culture, Urine lytes, Chest x-ray, Abdominal ultrasound with dopplers, diagnostic paracentesis if ascites is present) and performing urine pregnancy testing in women of child bearing potential. Subjects will be randomized 1:1 by the Investigational Pharmacy.

Subjects will then take a 14-day course of PTX 400 mg three times a day. On day 3 there will be an in-person assessment and review of side effect profile. If there have been no serious adverse events, PTX will be continued. Additional safety assessments will be completed at day 7,10,14.

Patients will also be seen in the hospital to assess for treatment response at day 3,7,10,14. At these visits, they will have repeat blood work at the discretion of the treating physicians (e.g. CBC, CMP, INR, UA with reflex urine culture, Urine lytes,). During each assessment, primary and secondary endpoints will be measured. If an endpoint is obtained, the patient will be instructed to stop therapy.

Survival will be assessed at 30 and 180 days by telephone interviews. If subjects are discharged prior to completing 14 days of therapy, they most likely has met an endpoint (resolution, death, transplant, etc). If in the unlikely event the patient is to be discharged and they have not met an endpoint, they will be withdrawn from the study. Once the patient is discharged there will be no in person follow up evaluations.

Figure 1: Study protocol

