### 3. Subject Selection

This study will enroll 30 patients with cirrhosis hospitalized with acute or chronic liver disease and ARF as defined according to the criteria put forth by and validated prospectively by collaboration between the International Ascites Club (IAC) and the Acute Dialysis Quality Initiative as a rise in creatinine of 0.3 mg/dl or 50% from baseline creatinine, which will be defined as the most recent stable measurement before admission.[1]

All participants will be aged greater than or equal to 18 and non-pregnant because of the study drug characteristics. Patients with labeled contraindications to PTX use will be excluded.

All subjects will be initially located on the general medical floor, typically 5 central which is a GI and hepatology floor. If a subject decompensates and requires ICU level care then they will be transferred to the ICU at the discretion of the treating physician. Admission to the ICU will not impede participation status unless the patient reaches an endpoint of death, liver transplant or renal replacement therapy at which time their participation in the study will have concluded. We will not be performing initially enrollment of the patient in the ICU. We will not seek surrogate consent. If a patient is still in the ICU at day 14 they will not be considered for therapy beyond that point and therefore surrogate consent will not be required.

If a patient is unable to swallow a pill for 6 consecutive doses they will be withdrawn from the study.

Table 1 shows the exclusion criteria.

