### 7.2. Study Drug Discontinuation

Study drug or placebo will be discontinued if a grade 3 adverse event (based on the NCI Common Terminology Criteria for Adverse Events, CTCAE, version 4.0) related to the study drug at the judgment of the PI and medical monitor. The PI will notify the medical monitor of a grade 3 adverse event over the phone and the medical monitor will conduct an independent review with access to the medical record. The medical monitor may interview the patient at the bedside should they deem this necessary. Meetings between the medical monitor and the PI will take place on an as needed basis. One scheduled meeting will take place after 50% enrollment has been completed to review all the reported adverse events.

Study drug or placebo will be discontinued if a grade 4 adverse event or pregnancy occurs during the study protocol or at the request of the subject. If the subject misses a dose and is less than 4 hours late, the subject will be advised to make up the dose. Otherwise, the dose can be omitted and per protocol dosing can resume with the next scheduled administration.

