#### 10.4.1. Serious Adverse Events

Following the subject's written consent to participate in the study, all SAEs must be collected, including those thought to be associated with protocol-specified procedures. All SAEs must be collected that occur within 14 days of discontinuation of dosing of the study drug. If applicable, SAEs must be collected that relate to any later protocol specified procedure. The investigator will notify the local IRB of any SAE occurring after this time period that is believed to be related to the study drug or protocol-specified procedure. Serious adverse events, whether related or unrelated to study drug, must be reported within local regulatory requirements. An SAE report should be completed for any event where doubt exists regarding its status of seriousness.

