### 10.6. Study Termination, Monitoring, and Data Security

[name] will serve as the independent medical monitor for the study subjects. The PI reserves the right to terminate any subject from the protocol if he deems the study subject's continued participation will hinder the effective execution of the protocol or places the subject at risk that is not justified. If the SAE's occur in more than 25% of participants, the PI will place on hold further enrollment in the study until review by an independent local regulatory board composed of a Hepatologist, a Gastroenterologist, and another uninvolved physician vote unanimously to continue the study with appropriate binding modifications made and approved by the local IRB. The study database will be maintained on data systems behind secure university firewalls using state-of-the-art data security technology. The PI and sub-investigators will be the only people with access to the

study database and all protected personal data will be stored in a “linked and coded” dataset.

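### Exit rules that, read literally, end study participation conflict with the planned day-30 and day-180 survival follow-up, and resolution is not defined after a swallowing or PI exit

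*Combined protocol and SAP*

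**What the plan says.** Four rules take a subject out.

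- Section 2, which calls the case unlikely: if "the patient is to be discharged and they have not met an endpoint, they will be withdrawn from the study".
- Section 3: "If a patient is unable to swallow a pill for 6 consecutive doses they will be withdrawn from the study".
- Section 3, in the paragraph on ICU transfer: the endpoints listed are death, "liver transplant or renal replacement therapy at which time their participation in the study will have concluded".
- Section 10.6: "The PI reserves the right to terminate any subject from the protocol".

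Elsewhere the protocol has wording that stops only the drug. Section 2: "If an endpoint is obtained, the patient will be instructed to stop therapy". Section 7.2: "Study drug or placebo will be discontinued if a grade 4 adverse event or pregnancy occurs during the study protocol".

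On analysis, the Synopsis and Section 9 both specify intention to treat. The Synopsis lists transplant-free survival and overall survival as separate endpoints, each at days 30 and 180. Section 9 plans Kaplan-Meier curves and a log-rank test for all-cause mortality. Section 2 and Table 2 provide telephone contact at days 30 and 180 and make no exception for subjects who have left.

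Some outcomes after an exit are covered. For subjects enrolled at stage III, "they will be considered to have progressed should they be started on renal replacement therapy (RRT"). Partial response requires no dialysis. Transplant is an event for transplant-free survival.

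**The concern.** The exit rules and the survival plan cannot both be followed literally. Staff who treat a subject as withdrawn, or as having concluded participation, could reasonably make no day-30 or day-180 call. Vital status would then be missing for subjects who left because they could not swallow, started RRT, were transplanted or were removed by the PI. These events are plausibly related to prognosis, so Kaplan-Meier censoring at them would plausibly be informative. Censoring subjects who later die raises that arm's survival estimate; censoring transplanted subjects who survive lowers it.

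Transplant is the clearest case. Overall survival differs from transplant-free survival only through what happens after transplant, which is where Section 3, taken literally, stops. This needs no assumption about how many subjects exit.

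The primary endpoint has a smaller gap. A subject discharged without an endpoint has, by that description, not resolved. After a swallowing or PI exit, however, no passage says how resolution is scored. Such an exit can come early: at the Synopsis dosing frequencies, six doses take 6/3 = 2, 6/2 = 3 or 6/1 = 6 days of the 14.

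**Working it through.** **Which outcomes are left open, by exit**

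| Exit | Overall survival | Resolution |
|---|---|---|
| Death | Settled | No explicit rule; not part of this point |
| Transplant | Open (transplant-free survival is settled) | No explicit rule |
| RRT | Open | No explicit rule; counts as progression for stage III enrollees |
| Discharge without an endpoint | Open | Not resolved, by description |
| Swallowing failure | Open | Open |
| PI termination | Open | Open |

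**Inputs.** Section 9 gives 30 subjects, 15 per arm. It gives no exit rate, survival rate or resolution rate, so there is no figure in the plan to reproduce beyond 15 + 15 = 30. Everything below except the arm size is assumed. One subject is 1/15 = 6.7 points of an arm.

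**Survival illustration.** Assume that true day-180 survival is 7/15 = 46.7% on placebo and 10/15 = 66.7% on PTX, a difference of 20.0 points. Suppose that x subjects who will later die are censored early, after d deaths in their arm (d = 0 to 2), and that everyone else is followed to day 180. With s true survivors, the Kaplan-Meier estimate is

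S = (15 − d)/15 × s/(15 − d − x).

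- Placebo, x = 1: from 7/14 = 50.0% (d = 0) to 13/15 × 7/12 = 50.6% (d = 2). Difference 16.7 to 16.1 points.
- Placebo, x = 2: from 7/13 = 53.8% to 13/15 × 7/11 = 55.2%. Difference 12.8 to 11.5 points.
- PTX, x = 1: from 10/14 = 71.4% to 13/15 × 10/12 = 72.2%. Difference 24.8 to 25.6 points.
- PTX, x = 2: from 10/13 = 76.9% to 13/15 × 10/11 = 78.8%. Difference 30.3 to 32.1 points.
- One in each arm, d = 0: 71.4% − 50.0% = 21.4 points.

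**Censoring at transplant.** If t PTX subjects alive at day 180 are censored at an early transplant, S = (15 − d)/15 × (10 − t)/(15 − d − t). For t = 1 this runs from 9/14 = 64.3% to 13/15 × 9/12 = 65.0%. For t = 2 it runs from 8/13 = 61.5% to 13/15 × 8/11 = 63.0%. The true value is 66.7%.

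**Primary endpoint, one PTX exit.** Take 9 PTX resolvers plus one exit against 3/15 on placebo. Fisher's two-sided p is 0.060 with the exit as non-resolution (9/15), and 0.025 with it excluded (9/14) or counted as resolved (10/15). Against 2/15 the values are 0.021, 0.008 and 0.008; against 4/15 they are 0.139, 0.066 and 0.066. Over all 16 × 15 = 240 count pairs with one PTX exit, the handling changes whether p < 0.05 in 22 (9%). In 11 of those 22 the change appears only if the exit is counted as resolved.

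**The case against.** The best defence is that the exit wording means the end of treatment and in-hospital assessment only. The survival calls are unconditional, the absence of in-person visits after discharge is compatible with telephone contact, and listing overall survival apart from transplant-free survival implies follow-up past transplant. The Section 3 sentence on concluded participation is about ICU transfer. Figure 1 is not available to this review and may bear on it. This makes continued follow-up a plausible intention. It does not settle the matter, because the protocol uses drug-only wording elsewhere and chose broader wording for these exits.

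A reader might infer that exited subjects are to be dropped from the analysis. The documents do not support that. Withdrawal does not by itself breach intention to treat, and both the Synopsis and Section 9 say that intention to treat applies.

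A reader might also infer from the Fisher figures that the plan leaves the primary result free to cross 0.05. That is too strong. Excluding an exit would contradict the stated population, and counting it as resolved without a demonstrated 24-hour return to baseline would contradict the endpoint definition. Non-resolution is the natural default, and 218 of the 240 pairs (91%) are unaffected anyway.

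The one-arm survival scenarios are also the unfavourable ones. In a blinded trial, similar exits in both arms would largely offset. The assumed 10/15 against 7/15 has Fisher p = 0.46, and no change in a log-rank conclusion has been shown.

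**Conclusion.** The conflict is real and should be fixed. The exit rules, followed as written, end follow-up at unresolved discharge, swallowing failure, transplant and RRT, while the survival plan needs vital status at days 30 and 180 for all randomised subjects. PI termination is unclear on the same point. The consequence for overall survival after transplant follows from the text alone.

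The numerical size is only illustrative. It depends on an unknown number of exits, on their timing, on their later outcomes and on how evenly they fall between arms. One or two early exits confined to one arm move an assumed 20.0-point difference by roughly 3 to 12 points, in either direction; one in each arm moves it by 1.4 points. For the primary endpoint the gap is an unwritten scoring rule for swallowing and PI exits, not evidence that the result would be distorted. Confidence is medium, because the unconditional calls suggest that follow-up may have been intended all along.

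**What to change.** Leave the dosing and drug-stopping rules unchanged.

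- **Sections 2 and 3:** reword the sentences on unresolved discharge, swallowing failure, and transplant or RRT so that these exits do not end survival follow-up. In Section 10.6, clarify that PI termination does not end it either.
- **Sections 2 and 8:** state that the planned day-30 and day-180 calls are made for every randomised subject unless consent is withdrawn, including after transplant, RRT, a swallowing exit, early discharge or PI termination.
- **Section 9:** state that overall survival is not censored at transplant or RRT. State that exited subjects stay in the intention-to-treat denominator and count as non-resolution unless available inpatient creatinine through day 14 shows a 24-hour return to baseline.

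The cost is wording, a few more calls and some chart checks. Some creatinine values may be absent, because Section 2 leaves repeat blood work to the treating physicians.

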### 3. Subject Selection

This study will enroll 30 patients with cirrhosis hospitalized with acute or chronic liver disease and ARF as defined according to the criteria put forth by and validated prospectively by collaboration between the International Ascites Club (IAC) and the Acute Dialysis Quality Initiative as a rise in creatinine of 0.3 mg/dl or 50% from baseline creatinine, which will be defined as the most recent stable measurement before admission.[1]

All participants will be aged greater than or equal to 18 and non-pregnant because of the study drug characteristics. Patients with labeled contraindications to PTX use will be excluded.

All subjects will be initially located on the general medical floor, typically 5 central which is a GI and hepatology floor. If a subject decompensates and requires ICU level care then they will be transferred to the ICU at the discretion of the treating physician. Admission to the ICU will not impede participation status unless the patient reaches an endpoint of death, liver transplant or renal replacement therapy at which time their participation in the study will have concluded. We will not be performing initially enrollment of the patient in the ICU. We will not seek surrogate consent. If a patient is still in the ICU at day 14 they will not be considered for therapy beyond that point and therefore surrogate consent will not be required.

If a patient is unable to swallow a pill for 6 consecutive doses they will be withdrawn from the study.

Table 1 shows the exclusion criteria.

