## **Brief Study Synopsis**

**Study Phase:** Pilot

**Primary hypothesis:** Pentoxyfylline (PTX) therapy at 1200 mg per day or the renally dose equivalent in addition to standard of care is superior to placebo in the treatment of acute renal failure (ARF) not responsive to volume resuscitation in hospitalized patients with cirrhosis.

**Study design:** Prospective, placebo-controlled, randomized pilot trial.

Each hospitalized subject will undergo pre-dosing screening with review of his or her history and physical exam from the day of enrollment and safety assessment to ensure no contraindication to use of PTX.

ARF will be defined according to the definition put forth by and validated prospectively by collaboration between the International Ascites Club (IAC) and the Acute Dialysis Quality Initiative as a rise in creatinine of 0.3 mg/dl or 50% from baseline creatinine, which will be defined as the most recent stable measurement before admission.[1]

Baseline testing will be obtained from hospitalization records, including but not limited to chemistry panel, liver function testing, urinalysis, urine electrolytes, coagulation studies, blood cultures, chest x-ray, diagnostic paracentesis, abdominal ultrasound with Doppler.

Subjects will take either placebo three times a day or PTX 400mg three times a day or 400mg twice a day for eGFR 10-50 and 400mg once a day for eGFR <10 for 14 days in addition to standard inpatient care. Treatment will be continued for 14 days unless a study endpoint has been reached at which time either PTX or placebo will be stopped.

**Total study subjects expected:** 30 patients with cirrhosis hospitalized ARF

**Duration of study:** 180 days

**Study Drugs:** PTX 400 mg tablets and placebo. The study team will not be pursuing a change in labeling or an FDA approved indication for this drug as a part of this proposal. Standard placebo provided in similar tablet forms. All investigational drugs will be prepared by the Investigational Pharmacy by inserting the active drug/placebo into larger cloaking capsules. Standard corn starch will be used inside the placebo capsule.

Randomization will be 1:1. The Investigational Pharmacy will be performing randomization and will generate the block randomization scheme.

**Endpoints:** The primary endpoint is resolution of ARF, defined as a return to baseline creatinine for 24 hours.

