## 7. Study Treatments

### 7.1. Investigational Drug

PTX is a vasoactive xanthine derivative and phosphodiesterase inhibitor that improves peripheral blood flow and enhances peripheral tissue oxygenation. PTX relaxes smooth muscle in peripheral vessels leading to vasodilation. PTX improves red blood cell flexibility, which allows for improved blood flow ability. Importantly, PTX promotes platelet deaggregation and decreases blood viscosity. The summative effects are a decrease in inflammatory mediators. The investigational pharmacy will be used for drug acquisition, storage, and accountability. Subjects will start the protocol with 400mg PTX three times a day for 14 days or the renally dosed equivalent (400mg BID for eGFR 10-50 and 400mg daily for eGFR <10). The investigators will not seek FDA labeling or approved indications for PTX as part of this study; therefore, no IND will be sought for the study drug use in this protocol. There are no restrictions on concurrent drugs other than those listed in the exclusion criteria in Table 1. The study drug cannot be crushed or administered through a nasogastric tube. If a patient is NPO but can swallow safely, they may receive the drug. If they are NPO and have a nasogastric tube in place they will miss the dose.

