## 9. Statistical Procedures and Methods

As this is a pilot study and the benefit of PTX in the treatment of ARF has not been studied, we estimate a sample size of 30, 15 in each treatment arm, is sufficient to meet our primary and secondary endpoints. Results will be expressed as means with standard deviations. Chi-squared and Fisher's exact test will be used to analyze our categorical endpoints. Student's t test and Mann-Whitney Rank Sum test will be used for secondary analysis of differences in numerical lab data. Kaplan-Meier curves will be constructed and compared by a log-rank test to assess our secondary endpoint of all-cause mortality. A p value of  $<0.05$  will be significant. Intention to treat analysis will be performed. Subgroup analysis will be performed by stratifying on initial AKIN stage.

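### Patients who cannot swallow six doses in a row, or who go home without an endpoint, leave the study itself, and nothing says how their outcomes are collected or counted under intention to treat

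*Combined protocol and SAP*

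**What the plan says.** Section 3 (Subject Selection) sets the rule: "If a patient is unable to swallow a pill for 6 consecutive doses they will be withdrawn from the study". Section 7.1 shows how doses come to be missed: "The study drug cannot be crushed or administered through a nasogastric tube". A fasting patient with such a tube in place misses the dose, although a fasting patient who can swallow safely may take it.

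Section 2 (Study Design) has a parallel rule. A patient discharged before day 14 without an endpoint, which the plan thinks unlikely, is also withdrawn from the study.

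Section 7.2 treats safety events differently: "Study drug or placebo will be discontinued if a grade 4 adverse event or pregnancy occurs during the study protocol". That wording stops the drug and does not mention leaving the study.

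On analysis, the Synopsis says "All analyses will be conducted based on the intention to treat population" and Section 9 says "Intention to treat analysis will be performed". The primary outcome is a creatinine outcome: "The primary endpoint is resolution of ARF, defined as a return to baseline creatinine for 24 hours". It is assessed in hospital on days 3, 7, 10 and 14, and survival is assessed by telephone on days 30 and 180. At the hospital visits, "they will have repeat blood work at the discretion of the treating physicians".

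**The concern.** Being unable to swallow is a reason to stop a capsule. It is not a reason to stop observing creatinine or survival. As written, a patient with a grade 4 adverse event stops the drug only, while a patient who cannot swallow for two or three days leaves the study.

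Intention to treat fixes who is analysed and in which arm. It does not supply a value for an outcome that was not observed, and the plan has no rule for missing or withdrawn outcomes. The analyst would have to choose, after the data are in, between leaving these patients out, counting them as not resolved, or going back to the chart.

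The loss is unlikely to be random. Patients who cannot swallow for that long are probably sicker than the others, so leaving them out would tend to overstate resolution rates, and censoring their survival at withdrawal could be informative. That they are sicker is a clinical assumption, not something the documents state. It does not extend to patients discharged without an endpoint, who may differ in other ways.

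**Working it through.** There is no stated figure to reproduce here: the plan gives no withdrawal rate, resolution rate or rate of swallowing problems. The check is a reading of the text plus simple arithmetic.

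**Inputs.** Six consecutive doses (Section 3); three times daily, twice daily for eGFR 10-50, once daily for eGFR below 10 (Section 7.1); a 14-day course (Synopsis); 30 patients, 15 per arm (Section 9).

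**1. How soon the rule takes effect.** Time to six missed doses = 6 / doses per day.
- Three times daily: 6/3 = 2 days
- Twice daily: 6/2 = 3 days
- Once daily: 6/1 = 6 days

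All fall well before day 14, so the rule can end participation while the primary outcome is still open.

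**2. What is provided after each event.**

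| Event | Consequence | Later outcome collection stated? | Classification stated? |
|---|---|---|---|
| Cannot swallow six doses (Section 3) | Leaves study | No | No |
| Discharged without endpoint (Section 2) | Leaves study | No | No |
| Grade 4 event, pregnancy or subject request (Section 7.2) | Drug stopped | Study exit not mentioned | Not addressed |

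The first two rows are where the plan departs from what its intention-to-treat statements need.

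**3. What one lost outcome is worth.** If r patients are known to have resolved and one of 15 is unknown, the arm's rate lies between r/15 and (r + 1)/15. The width is 1/15 = 0.067, or 6.7 percentage points. With one unknown in each arm, the difference between arms is uncertain by 2/15 = 0.133, or 13.3 points.

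Illustration with assumed counts: 9 of 14 against 3 of 14 observed, one unknown per arm.
- Largest difference: 10/15 - 3/15 = 7/15 = 46.7 points
- Smallest difference: 9/15 - 4/15 = 5/15 = 33.3 points

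The gap is 13.3 points, as the formula gives. It shows the weight of each outcome in a trial of this size and does not predict the result.

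**The case against.** The strongest reply is that little may actually be lost. Intention to treat already keeps these patients in the denominator. Those who cannot swallow will usually still be inpatients, so creatinine will probably be in the chart. Eligibility also limits the numbers: nobody is enrolled in the ICU, and shock and a life expectancy of 72 hours or less are exclusions. All of this stands, and it is why the point is only that outcomes may be lost. It does not close the gap, because no section plans to collect or use those values after withdrawal.

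A reader might infer four stronger points that the documents do not support.

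- **A conflict with the ICU rule.** Section 3 also says "Admission to the ICU will not impede participation status unless the patient reaches an endpoint of death, liver transplant or renal replacement therapy". The two sentences are compatible: ICU admission alone does not end participation, and an ICU patient who can swallow stays in.
- **A built-in difference between arms.** Read literally, the Synopsis gives placebo three times daily while reducing active dosing by eGFR, so placebo patients would reach six doses sooner. Sections 2 and 7.1 do not confirm that reading, matched dosing would remove the difference, and the direction of any bias would still be unknown.
- **That the handling decides significance.** With assumed counts, Fisher's p is 0.047 for 9/13 v 3/13 and 0.060 for 9/15 v 3/15. Uncorrected chi-squared gives 0.018 and 0.025, so nothing changes. The plan names both tests and gives no resolution rates. Such examples mainly show how small the trial is.
- **A forecast of withdrawals.** Any such number would rest wholly on assumed frequencies and durations of swallowing problems.

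**Conclusion.** The concern holds in a limited form and is minor. Two rules remove patients from the study rather than from study drug alone, and the plan does not say how their outcomes are collected or classified, although it commits to intention to treat. Each lost outcome costs 6.7 percentage points of an arm of 15. How many patients would be affected, and whether the comparison would favour either arm, cannot be determined from the documents. The exact dose timings and the 1/15 weight follow from the text. That patients unable to swallow are sicker, and that outcomes would in practice go uncollected, are assumptions.

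**What to change.** **Section 3.** Replace withdrawal from the study with discontinuation of study drug. Continue to abstract creatinine, renal replacement therapy and transplant from the hospital record to day 14 or discharge, make the planned day 30 and 180 calls, and analyse these patients as randomised.

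**Section 2.** For patients discharged without an endpoint, keep the day 30 and 180 calls and count them in their randomised arm as not resolved at the last in-hospital assessment.

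**Cost.** A few sentences, a consent line saying that record review and calls continue after study drug stops, and a little record abstraction. No visits or patients are added, since the assessments and calls are already planned. Keeping patients who stopped the drug dilutes the contrast somewhat, which intention to treat accepts. Some creatinine values may still be missing because blood work is left to the treating physicians, but the protocol would no longer end follow-up itself.
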